
Aim 2: Cost. With N=131 available per arm (N=262 total) and α =0.05 we have 80% power to detect differences in mean cost per participant of 0.35 SDs. For example, if the SD for cost is \$100, then we have 80% power to detect differences in mean cost per participant of \$35.

Aim 3: Predictors (exploratory). With N=131 available per arm (N=262 total) and α =0.05 for continuous predictors we have 80% power to detect correlations of 0.243 with 12-month percent weight loss. With N=131 available per arm (N=262 total) and setting α =0.05, for categorical variables, detectable differences in mean percent weight loss depend on the proportion of the predictor in the sample. For a predictor with 50% prevalence (i.e., n=65 and n=66 with vs without the characteristic), we have 80% power to detect differences of 0.49 SDs. For predictors with 33% prevalence, we can detect differences of 0.52 SDs. For predictors with 20% prevalence, 0.62 SDs, and for predictors with 10% prevalence (i.e., n=13 vs n=118), 0.82 SDs. For estimated SD=5.5% for 12-month percent weight loss, this indicates differences of 2.7%, 2.9%, 3.4%, and 4.5% weight loss, respectively. Sample size calculations for Aims 2 and 3 were conducted using Stata.

For EACH Participant Population State Describe the Study Population(s): [Describe the participant population(s) including gender, ethnicity, income, level of education and age range.]

We will be recruiting from a representative population of individuals that live or work around Worcester MA and Storrs CT. We are recruiting men and women of all ethnicities, income and education levels between the ages of 18 and 65. Thus far we have had less success recruiting minorities and men and have put additional effort towards that goal. We will recruit participants in 9 waves off set by 2-3 months each. Waves 1-6 were recruited and carried out at UMass and waves 7-9 will be recruited and carried out at UConn.

We will also collect intervention delivery and feedback data from the interventionists. Interventionists are trained in the delivery of the DPP and are set up as consultants.

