Participants will complete follow-up visits at 6- and 12-months. The visit will last 1 hour and will include a weight measurement, blood pressure reading, three 24-hour diet recall interviews, and repeated baseline measures. The online survey containing the measures will be e-mailed to participants 1 week prior to the scheduled follow-up visits.

Time Commitment:

Visit	GS Condition	TC Condition
	(in minutes)	(in minutes)
Telephone Screening (20 min)	20	20
Baseline (210 min total)	210	210
Visit (90 min)		
2 at-home dietary recalls (60 min)		
Online survey (60 min)		
Webinar (60 min)	60	60
Orientations	180	

GS: individual orientation (60 min)		
GS: group orientation (120 min)		
TC: group orientation (60 min)		
Intervention	750	1980
GS: approx. 35 min/week 8 weeks, 14 min/week		
for 16 weeks, 8 min/week for 28 weeks (12.5 hrs)		
TC: 22 1.5 hr groups (33 hrs)		
6-month (150 min total)	150	150
Visit (30 min)		
2 at-home dietary recalls (60 min)		
Online survey (60 min)		
12-month (150 min total)	150	150
Visit (30 min)		
2 at-home dietary recalls (60 min)		
Online survey (60 min)		
Total	1520 minutes	2630
	(approx. 25 hrs)	2570 minutes
		(approx. 434
		hrs)

Interventionist data collection:

The interventionists provide the following information, some of which will be used in the analysis:

- Weekly timesheets for invoicing their time (these hours are used to calculate time/cost needed to deliver the intervention aim 2).
- A 10 minute survey at the end of each 6-month phase for each wave used to gather interventionist feedback.

Measures

Data Collected	List of Measures	Baseline	During	6	12	Method
			Intervention	Months	Months	
BMI	Height	Х				REDCap
	Weight	Х	X (weekly)	Х	Х	REDCap
Medications	Brief Medication Questionnaire ¹⁰	Х		Х	X	REDCap
Blood pressure	Blood Pressure	Х		Х	Х	REDCap
Demographics	Income, employment, marital status, race/ethnicity, household composition*	Х				REDCap
Medical History	Assesses exclusionary medical conditions*	Х				REDCap
Personality factors neuroticism/ openness	Ten-Item Personality Inventory (TIPI) ¹¹	Х				REDCap
Binge Eating Disorder	SCID Interview ¹² for BED	Х				Interview
Physical Activity	Arizona Physical Activity Questionnaire ¹³	Х		Х	X	REDCap
Sleep Quality	STOP ¹⁴	Х		Х	Х	REDCap
	Insomnia Severity Index ¹⁵	X		X	X	REDCap
	Pittsburgh Sleep Quality Index Questions ¹⁶	Х		Х	X	REDCap

	History of sleep apnea diagnosis*	X		X	X	REDCap
	Previous or current treatment for sleep apnea*	X		X	X	REDCap
Depression	BDI ¹⁷	Х		Х	X	REDCap

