We will compare total intervention costs per participant and total intervention costs per pound lost by treatment condition. We will conduct sensitivity analyses to estimate the range of costs after varying the inputs (e.g., time spent on Twitter by participants, staff pay across settings and based on qualifications and training). We will also examine administrative, interventionist, and participant costs by treatment condition. Assuming a normal distribution of total costs per participant, we will first compute t-tests comparing the average cost per participant across treatment conditions. We will test the null hypothesis of no difference between groups using a two-sided test and α =0.05. If total cost per participant is not normally distributed, a non-parametric approach using the Mann-Whitney test for median comparisons will be used. If participant characteristics are found to differ according to treatment allocation/condition, multivariable models will be used to adjust for the potential confounding effects of these characteristics. Assuming a normal distribution of total costs per participant, multivariable linear regression models will be used. If not normal, we will identify appropriate transformations (e.g., logarithm, square root) for the cost variable.

Exploratory outcomes (treatment retention, acceptability, and burden)

We will compare treatment retention (percent retained in treatment, i.e., percent who has not dropped out of treatment) and ratings of acceptability and burden (measured on 5-point Likert scales) across treatment conditions using χ^2 tests.

Predictors of weight loss in the Get Social condition (exploratory)

Bivariate associations between each potential predictor of weight loss (e.g., engagement, age, sociability, neuroticism, openness, smartphone and online social network use) and percent weight loss at 12 months will be examined among participants in the Get Social condition using linear regression models. Multivariable predictors of percent weight loss at 12 months will be estimated using linear regression models. Variables will be added to the model one at a time, in order of magnitude of the crude effect estimate (largest to smallest; p<0.05) associated with the outcome. The final model will be selected based on consideration of effect estimates, 95% confidence intervals, and Akaike information criterion (AIC).

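### The exploratory predictor model enters variables by size of crude estimate with no stated scale and a p<0.05 filter, so entry order can depend on coding and selected estimates are biased away from zero

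*Protocol*

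**What the plan says.** The only specification is in the Protocol, Data Analysis, under *Predictors of weight loss in the Get Social condition (exploratory)*. The SAP has no predictor section.

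- Candidates are given as examples: "e.g., engagement, age, sociability, neuroticism, openness, smartphone and online social network use".
- The bivariate associations with 12-month percent weight loss "will be examined among participants in the Get Social condition using linear regression models".
- For the multivariable model, "Variables will be added to the model one at a time, in order of magnitude of the crude effect estimate". The parenthesis that follows reads "largest to smallest; p<0.05) associated with the outcome".
- The last step is: "The final model will be selected based on consideration of effect estimates, 95% confidence intervals, and Akaike information criterion (AIC".

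The section mentions no standardisation, shrinkage, validation or multiplicity handling. The candidates share no unit: participants are "between the ages of 18 and 65" years old, neuroticism and openness are personality scores, and engagement and use are measured in other ways again. The Aim 3 paragraph under Justification of Sample Size starts "With N=131 available per arm (N=262 total" and gives detectable effects for continuous and categorical predictors at 80% power.

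**The concern.** A bivariate linear regression yields a slope per unit of the predictor. If candidates are ranked on that slope, recoding age from years to decades multiplies its estimate by 10 and can move it up the entry order with no change in the data. A rare binary trait will outrank a common one of equal strength. When entry is sequential and the candidates are correlated, a different order can leave a different set of variables in the final model.

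The p<0.05 filter is a separate matter. A predictor that just passes tends to do so in a sample where its estimate is too large, and an ordinary 95% interval computed afterwards takes no account of that.

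Aim 3 carries directional hypotheses, and the protocol's background says the predictor work is meant to show whom the online modality suits. Readers may therefore use the list of retained predictors and their sizes.

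**Working it through.** **Inputs from the protocol (Justification of Sample Size).** n = 131 in the Get Social arm; alpha 0.05; 80% power; detectable correlation 0.243; outcome SD 5.5 points; detectable categorical differences 0.49, 0.52, 0.62 and 0.82 SD at prevalences 50%, 33%, 20% and 10%. Predictor SDs and true correlations are not in the documents and are marked as assumed below.

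**1. Reproduce the protocol's figure.** Fisher z, two-sided: r = tanh((1.960 + 0.842)/sqrt(131 − 3)) = tanh(0.2476) = 0.243. It reproduces with n = 131 and not with n = 262, which gives 0.172.

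**2. Equal strength, unequal crude estimate (binary predictors).** With prevalence p, d × sqrt(p(1−p)) puts the difference on approximately the correlation scale.

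| Prevalence | d (SD) | d × 5.5 (points) | d × sqrt(p(1−p)) |
|---|---|---|---|
| 50% | 0.49 | 2.7 | 0.245 |
| 33% | 0.52 | 2.9 | 0.245 |
| 20% | 0.62 | 3.4 | 0.248 |
| 10% | 0.82 | 4.5 | 0.246 |

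All four are about as strong as each other and as r = 0.243. Ranked by crude difference they spread from 2.7 to 4.5 points, on prevalence alone.

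**3. The same for a continuous predictor.** At r = 0.243 the slope is 0.243 × 5.5 = 1.34 points per SD. For age with an assumed SD of 12 years, that is 1.34/12 = 0.11 per year, or 1.11 per decade. For SDs of 14 and 10 years it is 0.10 and 0.13 per year. In years, age ranks about 24 times below the equally strong 50%-prevalence contrast (2.7/0.11).

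**4. A reversal among predictors that pass the filter (assumed values).** Age with r = 0.30 and SD 12 years has a slope of 0.30 × 5.5/12 = 0.14 per year, or 1.38 per decade. A score with r = 0.22 and SD 1.2 has a slope of 0.22 × 5.5/1.2 = 1.01 per point. The stronger predictor enters second in years and first in decades.

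**5. Can order change the final set?** The p-values and AIC do not depend on units, so order matters only if selection is sequential. As an illustration, 4,000 samples of n = 131 were simulated with seven candidates, pairwise correlation 0.3, and true standardised slopes 0.20, 0.15, 0.10, 0.10, 0, 0, 0 (all assumed). Candidates passing p<0.05 were entered in order of slope and kept if AIC improved. Two choices of units gave different final sets in 2,724 of the 3,912 samples where at least two candidates passed (70%). The keep rule is also an assumption, so this shows that the effect can occur and does not forecast its frequency here.

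**6. Inflation from the filter.** With a critical t of 1.979 on 129 df, the smallest significant |r| is 1.979/sqrt(129 + 1.979²) = 0.172, or 0.172 × 5.5 = 0.94 points per SD (using unrounded r). Simulating 100,000 samples of n = 131 at each true correlation, the mean crude slope among significant results divided by the truth was:

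| True r | 0.10 | 0.15 | 0.20 | 0.243 | 0.30 |
|---|---|---|---|---|---|
| Ratio | 2.18 | 1.55 | 1.25 | 1.12 | 1.04 |

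These ratios are for single-predictor slopes. Adjusted slopes from the same data share the direction of the bias, but their size depends on correlations that the documents do not give.

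**The case against.** - **Scale.** A reader might infer that the protocol ranks on raw coefficients. It does not say so. Crude here means unadjusted, and the sample size section expresses Aim 3 effects as correlations and SD differences, so ranking on a standardised size is a possible reading. This stands: the fault is that the scale is unspecified, with the per-unit slope as the natural reading.
- **Final choice.** The final model rests on estimates, intervals and AIC, not on order alone. If AIC were compared across all subsets of the filtered variables, units would not matter. That is correct, but the text describes one-at-a-time entry, and weighing three criteria without a rule does not remove the order effect.
- **Reach of the unit problem.** A reader might infer that units decide which predictors pass p<0.05. They do not; they affect order only.
- **Size of the inflation.** A reader might infer that all reported effects would be badly overstated. At the protocol's own detectable effect the inflation is about 12%, and it is 4% at r = 0.30. It is large only for weak predictors. All bivariate associations are also to be examined, so unselected crude estimates would be available if they are reported.
- **Multiplicity.** With seven independent null candidates, the chance that at least one passes is 1 − 0.95^7 = 30%. That is no argument for the change below, because seven unadjusted 95% intervals from one full model carry about the same chance.
- **Status.** The analysis is labelled exploratory. That stands and limits the weight of the point.

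**Conclusion.** The point holds as a cheap improvement to an exploratory aim. As written, the entry order has no defined scale. On the natural reading it depends on units and prevalence: the protocol's own equally detectable effects appear as 4.5 points, as 2.7 points, or as about 0.11 points per year of age (assumed SD 12 years). This reaches the final model only through sequential selection, which is the procedure described. Separately, the filter inflates selected estimates by about 12% at a true r of 0.243, 4% at 0.30 and 55% at 0.15, and ordinary 95% intervals ignore the selection. The inflation figures assume n = 131 and a filter applied to the crude association.

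The documents do not support reading this as a threat to the trial's main conclusion. The primary non-inferiority result and the sample size do not depend on this model.

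**What to change.** Replace the entry procedure with one prespecified linear model for 12-month percent weight loss in the Get Social arm. It should contain all the named baseline predictors (age, sociability, neuroticism, openness, smartphone use and social network use), with continuous predictors expressed per SD and no entry selection. Report every coefficient with its 95% CI. Engagement is measured during the intervention according to the protocol's measures table, so report it in a second model that adds it to these six. With 131 participants that gives 131/6, about 22 per variable, in the first model and 131/7, about 19, in the second.

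Place the wording in the SAP, which now has nothing on Aim 3. The cost is a sentence or two and no new data. The downside is that weak predictors stay in and use a few degrees of freedom. The change removes the unit dependence and the selection bias but not the multiplicity, so the results should stay labelled exploratory.

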Participants will complete a telephone screening, an in-person baseline, and an online webinar (described above). Eligible participants will then be randomized to one of two 12-month weight loss interventions: online (Get Social) or in-person (Traditional). Follow-up assessments will occur at 6- and 12-months.

Randomization: Randomization will take place after the baseline procedures are complete once we've determined eligibility. Participants will be randomized to the Get Social or the Traditional condition. We will randomize 36-40 participants for each recruitment wave, for a goal of approximately 18 per condition. Participants will be randomized 1:1 to the two study conditions in randomly permuted blocks of size 4 and 6 using the ralloc program in Stata Randomization and will be stratified by gender (male vs. female) and baseline BMI (27.0-34.9 vs. 35.0-45.0). The randomization list was generated at the start of the study before randomization. The list is managed by the program director. Once a participant has been determined to be eligible, the program director will assign each participant to the next open assignment on the list. The program director will then tell the research assistant who will reach out to participants to inform them via e-mail of the condition assignment.

Orientation-Visits:

- Traditional participants: This in-person group will last 1 hour and will include training on The first session of the intervention will be extended from 1.5 hours to 2 hours in order to provide time for the orientation which will cover: -My Fitness Pal, an overview of their participation, and study goals. My Fitness Pal is an app that can be used to track diet and physical activity. It can be used on a computer or mobile app. Participants will receive their study goals for weight loss (1-2 lbs. per week), diet, and physical activity. The weight loss goal is approximately 7% weight loss over a 12 month period. This orientation may be completed on an individual in-person basis or phone for people unable to attend the group, though this option won't be encouraged. The weight loss goal is provided in the My Fitness Pal app. –The orientation group is led by the interventionist, a post-doctoral fellow, and a research assistant. and research assistants.

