Participants will be withdrawn from the study if: they drop from participation, do not complete all baseline procedures, disrupt in-person groups, or post inappropriate content on Twitter. Participants reporting that they would like to withdraw from the study will be given the option to: 1) withdraw from all intervention-related activity and contacts, but still complete the final assessment or 2) withdraw from the study completely with no additional study contact. If a participant becomes pregnant during the study, they will be withdrawn from the intervention, but will be given the option still complete the follow-up assessments.

Potential Harms/Risks and Inconveniences: [Describe the potential risks to participants (and secondary participants, if applicable) and **steps taken to minimize risks** for each participant population. Assess the likelihood of the risk occurring and, if it were to occur, the seriousness to the participant. Types of risks to consider include, but are not limited to: physical, psychological, social, legal, employment, and financial. Also describe any anticipated inconveniences the participants may experience (time, abstention from food, etc.).]

Possible risks for being in this study includes: Injury while exercising, breach of confidential information, and discomfort completing measures. The attempt to avoid risks to participants will be addressed by: suggesting moderate intensity exercise to avoid discomfort, pain, or injury. Participants reporting discomfort will be referred to their PCP. Injuries are unlikely to occur since we screen out medical conditions that could make someone prone to injury, we obtain medical clearance, and we only suggest moderate activity. We also provide participants with information on exertion level and remind them to see medical attention if there is pain. Tracking data will be stored electronically in REDcap, a network secure data entry program; any data on paper will be stored in a locked file cabinet; and participants will be informed that they may withdraw from the study at any time if they feel discomfort with any of the study procedures.

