Attendance will be collected at all study visits. If a participant misses a group, materials will be sent to them and a make-up session will be offered. If a participant chooses to drop from the intervention, they will be given the option to skip the rest of the intervention visits, but still complete the final assessment. Compliance information (number/percent of intervention visits attended; engagement in Twitter private group) will be provided in a report to the safety officers.

Data Security:

The databases will be maintained on UConn and UMass servers where security will be maintained through access controls. The program director will control the database and surveys and will allow access to necessary staff. Staff wanting access to identifiable data will need to: have prior IRB approval to be on the project, apply for a REDCap account, be approved by the program directo, and utilize a password for login.

Data review (completeness/outliers):

Data reports will be reviewed by the data manager, project director, statistician, and PI. Reports will include completeness of data (visits completed, online engagement, % of expected forms submitted, % of submitted forms passing edit); missed visits and missing information within visits; descriptive information for each endpoint (change in weight and physical activity) without statistical testing; and quality control analyses for primary outcome (change in weight).

Privacy/Confidentiality Part 1: [Explain how the privacy interests of participants will be maintained during the study (note that **privacy pertains to the individual not to the data**). Describe how data will be coded. Do not use the any potentially identifiable information such as initials of participants as part of the code. If identifiable, sensitive information (illegal drug use, criminal activity, etc.) will be collected, state whether a Certificate of Confidentiality will be obtained. Be sure to state whether any limits to confidentiality exist and identify any external agencies (study sponsor, FDA, etc.) that will have access to the data. If participants will be screened, describe the plans for storage or destruction of identifiable data for those that failed the screening.]

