2/26/2021

Statistical Analysis Plan

Study Title: Get Social: Randomized Trial of a Social Network Delivered Lifestyle Intervention

NCT02646618

Preliminary analysis

Baseline participant characteristics will be examined by condition. If groups differ on certain characteristics, these variables will be included as covariates in the primary analyses. Other preliminary analyses include assessing patterns of missing data, dropout rates, distributional properties of dependent measures, and correlations among outcome measures. A series of sensitivity analyses will be performed to examine the extent of potential bias by assuming the participants who dropped out are (i) missing completely at random (i.e., independent of the outcome), (ii) are responders to the intervention, or (iii) are non-responders to the intervention. Multiple imputation and other methods will be explore to address missing data for variables for which more than 5% of data are missing.

Primary non-inferiority outcome

We will model percent weight loss at 12 months using a linear mixed model, with percent weight loss as the dependent variable and study condition as the independent variable and accounting for repeated measures of weight. Test of the intervention condition indicator will provide a statistical test of the intervention effect and the estimated coefficient, along with the estimated confidence interval. This analytic approach aims to test whether the Get Social condition is not appreciably worse than (i.e., not inferior to) the traditional condition for percent weight loss at 12 months by our a priori inferiority margin of 2%. The effect estimates will reveal clinical non-inferiority of the Get Social condition if the confidence interval lies completely above $-\Delta$ or clinical non-inferiority of the traditional condition if the confidence interval lies completely below $+\Delta$, i.e., 2%.

Secondary non-inferiority outcomes

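### Removal for conduct ends study participation with no stated offer of follow-up weights, and dropping out as a ground for study withdrawal is not reconciled with the option to keep the final assessment

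*Protocol*

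**What the plan says.** The withdrawal paragraph follows the exclusion list in the Protocol's Inclusion/Exclusion Criteria. It has three parts.

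- **Grounds for withdrawal from the study:** "they drop from participation, do not complete all baseline procedures, disrupt in-person groups, or post inappropriate content on Twitter".
- **Participants who ask to stop:** "Participants reporting that they would like to withdraw from the study will be given the option to" choose between two routes. They may "withdraw from all intervention-related activity and contacts, but still complete the final assessment", or "withdraw from the study completely with no additional study contact".
- **Pregnancy:** "they will be withdrawn from the intervention, but will be given the option still complete the follow-up assessments".

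Under Data Safety Monitoring, Participant retention, the Protocol returns to people who choose to leave the intervention: "they will be given the option to skip the rest of the intervention visits, but still complete the final assessment".

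The schedule under Study Design is "Follow-up assessments will occur at 6- and 12-months", so the final assessment is the 12-month visit, which is the primary time point.

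The SAP models percent weight loss at 12 months with a linear mixed model that takes account of repeated weights. On missing data it says: "A series of sensitivity analyses will be performed to examine the extent of potential bias by assuming the participants who dropped out are" missing completely at random, responders, or non-responders. It will also explore multiple imputation and other methods for variables with more than 5% missing. Neither document says how participants removed by staff are followed up or analysed.

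**The concern.** Within one paragraph the Protocol separates leaving the intervention from leaving follow-up for pregnancy, but does not do so for conduct. Read as written, removal for conduct ends outcome collection. Each conduct ground belongs to one arm's delivery setting, so whether a 12-month weight exists could depend on the arm assigned. That is loss after randomisation in the comparison that decides non-inferiority.

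Two further gaps concern people who leave on their own account:

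- Dropping participation is a ground for withdrawal from the study, while the next sentence and the Participant retention section let people leave the intervention and keep the final visit. Both provisions speak of someone who reports a wish to withdraw or chooses to drop. A participant who stops responding is clearly caught only by the first rule.
- Those who do ask are offered only the final assessment, whereas pregnant participants are offered the follow-up assessments. Someone who leaves before 6 months therefore has no stated offer of the 6-month weight, although the SAP's primary model uses repeated weights.

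**Working it through.** **Which grounds can remove a primary outcome in an arm-related way**

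| Ground | Timing and arm | Follow-up offered in the text |
|---|---|---|
| Incomplete baseline | Before randomisation | Not relevant to arm-related loss |
| Drops participation | Either arm | Final assessment if the person asks to withdraw; unclear if they simply stop |
| Disrupts in-person group | Almost entirely Traditional (22 group sessions); Get Social has one 2-hour in-person group orientation | None stated |
| Inappropriate Twitter content | Get Social | None stated |
| Pregnancy (contrast) | Either arm | Follow-up assessments |

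The two conduct rows are therefore the arm-related gap.

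**Design inputs** (Protocol, Justification of Sample Size, Aim 1): margin 2 points, SD 5.5, true difference 0, alpha 0.05, power 90%, 131 evaluable per arm, 20% attrition, 164 per arm enrolled.

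Reproducing the plan's figure at one-sided 0.05: n = 2 × (1.645 + 1.282)² × 5.5² / 2² ≈ 130 per arm by the normal approximation, and 131 by the exact t calculation (power 90.2%). Then 131 / 0.80 = 163.75, so 164 per arm and 328 in total. The stated design reproduces.

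**Size of the conduct gap.** The documents give no number of conduct removals and no outcome gap, so both are assumptions:

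- w = extra share of one arm lost: 1-2%. Of 164 this is 1.6 to 3.3 people, about two or three.
- D = difference in mean percent weight loss between those kept and those lost: 3-5 points, direction not documented.

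Shift in a complete-case arm difference = w × D:

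- 0.01 × 3 = 0.03 points; 0.03 / 2 = 1.5% of the margin.
- 0.02 × 5 = 0.10 points; 0.10 / 2 = 5% of the margin.

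**Effect on the test**, with SE = 5.5 × √(2/131) = 0.680 and one-sided 0.05 (normal approximation):

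- Shift favouring Get Social, true difference at the margin: error rate = 1 − Φ(1.645 − shift/0.680). A shift of 0.03 gives about 5.5%, and 0.10 gives 6.7%, against a nominal 5%.
- Shift against Get Social, true difference zero: power = Φ((2 − shift)/0.680 − 1.645). A shift of 0.03 gives about 89.5%, and 0.10 gives 87.5%, against about 90%.

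**Precision.** If two or three people were lost from each arm beyond the planned 20%, 129 or 128 would remain per arm, with power (t-test) of 89.8% or 89.6%.

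**The case against.** The strongest reply is that the main route of loss is already handled. Anyone who tells staff they want to stop is offered the 12-month visit, in both the withdrawal paragraph and the Participant retention section. Only a person who chooses to end all contact is lost, and no rule could change that. This stands. A reader might infer that the Protocol discards the 12-month weights of dropouts in general; for people who ask to stop, the text says otherwise.

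The conduct grounds can also be seen as parallel, each covering misconduct in that arm's setting, and disruption in person is possible in Get Social because of its group orientation. That is correct, so the grounds are largely rather than strictly arm-specific. Parallel grounds still need not remove the same number or kind of participant.

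Conduct removals are probably rare. A reader might assume that 5-10% more of one arm is lost. That is about 8-16 of 164 people, and with nine waves and roughly one group per arm per wave it means one to two extra removals in every group. Nothing in the documents suggests that frequency. Nor do they show that people removed for conduct would have lost less weight, so the direction of any bias is unknown.

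Finally, the complete-case formula ignores the planned analysis. A mixed model with repeated weights, the three dropout scenarios and possible imputation would absorb part of the shift. This also stands, with two limits: the scenarios are framed around people who dropped out and do not mention removal by staff, and the model can use only weights that were collected.

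**Conclusion.** The point holds in a limited form, and its severity is low. The text offers no follow-up after conduct removal, on grounds largely tied to the assigned arm, and contrasts with its own pregnancy rule. It also leaves dropping participation unreconciled with the final-assessment option, leaves people who stop without asking uncovered, and omits the 6-month visit for those who ask.

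On the assumptions of 1-2% extra loss in one arm and a 3-5 point gap, the shift is about 0.03-0.10 points in a complete-case comparison, before any mitigation by the planned model and sensitivity analyses. That alone is unlikely to decide the trial unless the result falls very close to the margin.

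It would be tempting to claim a material gain in power from changing the rule. The documents do not support that: they do not attribute the planned 20% attrition to this rule, and inviting a few people removed for conduct could not recover much of it.

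**What to change.** In the withdrawal paragraph, state that:

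- after randomisation, removal by staff or dropping participation ends access to the group or Twitter feed only;
- every randomised participant, including those removed for conduct and those who stop without notice, is invited to both the 6- and 12-month weight visits unless they refuse further contact.

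Reconcile this paragraph with the Participant retention section so that both describe the same options. The conduct rules themselves stay unchanged.

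The cost is a short wording change plus a few follow-up visits already in each participant's schedule. Payments under Economic Considerations are at most $40 + $60 = $100 per person, so about $300 for three people in an arm. The documents contain no follow-up budget, so whether existing funds cover this cannot be judged from them.
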